# 7.3.3 Adverse Event Reporting Guidelines

All participating sites will report AEs to the Sponsor-Investigator per DF/HCC requirements, and the IRB of record for each site as applicable per IRB policies. The table below indicates which events must be reported to the DF/HCC Sponsor-Investigator.

	Table 6 DF/HCC Reportable Adverse Events (AEs)								
Attribution	Gr. 2 & 3 AE Expected	Gr. 2 & 3 AE Unexpected	Gr. 4 AE Expected	Gr. 4 AE Unexpected	Gr. 5 AE Expected or Unexpected				
Unrelated Unlikely	Not required	Not required	10 working days #	10 working days	24 hours*				
Possible Probable Definite	Not required	10 working days	10 working days#	10 working days	24 hours*				

# If listed in protocol or informed consent document as expected event does not need to be reported (except through routine reporting mechanisms)

# 7.4 Reporting to Bristol-Myers Squibb

Bristol-Myers Squibb (BMS) will also be informed of any serious adverse event (SAE) that occurs after the initial dose of study treatment, during treatment, or within 30 days of the last dose of treatment. Any SAE occurring after the reporting period must be promptly reported if a causal relationship in the investigational drug is suspected. Participant or partner pregnancy while on treatment or within 30 days of the last dose of treatment is also required to be reported to BMS via expedited reporting procedures.

Within 24 hours of first awareness of the event (immediately if the event is fatal or life-threatening), the study team will report to BMS by email ([contact]) any Serious Adverse Event ("SAE," as defined below) for which reporting is required under this provision (as described below). Such SAEs are to be reported for study subjects or individuals otherwise exposed to study drugs as described below. The study teams should report SAEs as soon as they are determined to meet the definition, even if complete information is not yet available.

SAEs to BMS will be reported on a SAE report form supplied by BMS and sent to the Sponsor-Investigator to review and report to [contact] on behalf of the reporting external site. Submissions should be made within 24 hours of the site's knowledge of the event.

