- 3.1.10 Willingness to provide pre-treatment tumor sample by core needle or excisional surgical biopsy. An archival sample is acceptable in the following situations: the sample was acquired within 90 days of initiation of PD-1 therapy AND the following provisions are met: 1) availability of a tumor-containing formalin-fixed, paraffin-embedded (FFPE) tissue block, 2) if the tumor containing FFPE tissue block cannot be provided in total, sections from this block should be provided that are freshly cut and mounted on positively-charged glass slides (SuperFrost Plus are recommended). Preferably, 25 slides should be provided; if not possible, a minimum of 15 slides is required. Exceptions to this criterion may be made with approval of the Study Chair.

DF/HCC Protocol #: 21-204 Protocol version date: v8/06 September 2023

3.1.11 Willingness to use contraception during and after study treatment. Women of child-baring potential (WOCBP) will be instructed to adhere to contraception for a period of 5 months following last dose of nivolumab and 6 months following the last dose of ipilimumab. Men receiving nivolumab and who are sexually active with WOCBP will be instructed to adhere to contraception for a period of 7 months after last dose of nivolumab and 6 months after the last dose of ipilimumab.

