# 7.4.2 Exposure During Pregnancy, Exposure During Lactation, Occupational Exposure

Even though there may not be an associated SAE, occupational exposure to ipilimumab +/-nivolumab or exposure during pregnancy or lactation is reportable to BMS.

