# 10.2 Required Data During Study

The following must be obtained during the study:

- Medical history, medication review, physical exam, vital signs, and weight, ECOG performance status (see Appendix A)
- Toxicity assessment
- CBC with manual differential, blood chemistries including complete metabolic panel, phosphorus, magnesium. These are required at each planned study visit -- day 1 of cycles 1-4, day 1 all maintenance cycles, day 43 of maintenance cycles.
- TSH, creatinine kinase, lipase, and triglycerides, as well as urine studies to include a urinalysis (and if urine protein positive >=2+, a 24-hour urine collection to quantify proteinuria). These are required at each planned study visit -- day 1 of cycles 1-4, day 1 all maintenance cycles, day 43 of maintenance cycles. Patients do need to meet laboratory eligibility criteria on C1D1 (see section 5.2).
- Pregnancy test at screening and D1 of each cycle (for women of childbearing age only).
- Peripheral blood sample for biomarker studies will be collected for research (see Section 9)
- Tumor restaging: PET/CT scans will be performed at baseline and after 4 doses of ipilimumab monotherapy (week 12). Among ipilimumab responders, restaging scans will occur prior to ipilimumab maintenance cycle 2 (week 24), cycle 3 (week 36), cycle 5 (week 60), and cycle 7 (week 84). Among ipilimumab non-responders, restaging scans will occur after 4 cycles of ipilimumab + nivolumab combination therapy (week 24) and prior to ipilimumab maintenance cycle 2 (week 36), cycle 4 (week 60), and cycle 6 (week 84). The end-of-treatment assessment will occur 4-12 weeks after the last doses of study therapy (i.e. weeks 112-120 for patients who complete all planned study therapy). Afterwards patients will be re-imaged every 24 weeks.

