PT/PTT/INR EKG	X X											Baseline
Concurrent Medications	X	X		X						 	X	Baseline N/A
Physical exam	X	X		X	X	X	(X)	X	X	X	X	At each study visit
Vital signs	X	X		X	X	X	(X)	X	X	X	X	At each study visit
Height	X											Baseline
Weight	X	X		X	X	X	(X)	X				Baseline, day

												1 induction and re- induction cycles and day 1 of each maintenance cycle
Performance status (Appendix A)	X	X		X	X	X	(X)	X	X	X	X	A each study visit
CBC w/diff, serum chemistry g	X	X		X	X	X	(X)	X	X	X	X	At each study visit g
TSH, creatinine kinase, lipase, triglycerides, urine dipstick for blood and protein h	Х	X		X	X	X	(X)	X	X	X	X	At each study visit h
Cheek swab/saliva sample		X										On Cycle 1 Day1
Peripheral blood collection for biomarker studies i		X		X	X		(X)	Xi	X	X		See footnote
Tumor biopsies k	$X^k$		(X) k							(X) k		See footnote
Radiologic Evaluation 	X						(X)	$X^{l}$		X	X	See footnote
Adverse Event Evaluation			X	XX								

a: Cycles 1-4 are 21 days

b: Patients who achieve an objective response after 4 cycles of ipilimumab therapy will proceed to maintenance ipilimumab treatment. Ipilimumab non-responders (who are clinically stable) will receive re-induction with ipilimumab and nivolumab.

c: Maintenance cycles are 12 weeks (84 days). (see section 5.1)

d: Follow-up evaluation. Patients will continue on treatment until disease progression, withdrawal of consent, adverse events preventing additional therapy, or completion of study therapy. After completing treatment, patients will have every 3-month visits for 2 years or until progressive disease, then every 6-month visits for 3 years. Survival follow-up will then continue to be captured every 6 months for 5 years or until participant withdrawal, death, or removal from study. Patient who receive subsequent anti-cancer therapy will be followed for relapse and survival (but will not require active follow-up and surveillance imaging on trial).

e: Pregnancy testing at screening and on D1 of each cycle (for women of childbearing age only)

- f: Consisting at a minimum of hepatitis C antibody, hepatitis B surface antigen and hepatitis B core antibody.
- g: See Sections 10.1 and 10.2. All tests will be required at screening.
- h: See Sections 10.1 and 10.2.
- i: Peripheral blood sample(s) will be collected for correlative studies per section 9
- i: See Section 10.3.

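### The explicit pregnancy reporting window in 7.4 closes 30 days after treatment, well short of the 5- to 7-month contraception periods in 3.1.11, and the Table 7 pregnancy-test cells conflict with their own footnote

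*Combined protocol and SAP*

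**What the plan says.** **Reporting.** Section 7.4 sets an explicit window: "Participant or partner pregnancy while on treatment or within 30 days of the last dose of treatment is also required to be reported to BMS". Section 7.4.2 adds, without any time limit, that "exposure during pregnancy or lactation is reportable to BMS", even where no SAE has occurred. Section 7.4 also asks for SAEs arising after the reporting period if a causal link to study drug is suspected, and 7.4.1 counts congenital anomaly or birth defect as an SAE.

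**Contraception.** Section 3.1.11 asks for "Willingness to use contraception during and after study treatment". Women of childbearing potential are to use "contraception for a period of 5 months following last dose of nivolumab and 6 months following the last dose of ipilimumab". Men receiving nivolumab who are sexually active with such women are to "adhere to contraception for a period of 7 months after last dose of nivolumab and 6 months after the last dose of ipilimumab".

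**Testing.** Section 10.2 requires: "Pregnancy test at screening and D1 of each cycle (for women of childbearing age only". Footnote e, attached to the B-HCG row of Table 7, says the same: "Pregnancy testing at screening and on D1 of each cycle (for women of childbearing age only". The cells of that row are marked at baseline and on day 1 of cycles 1 to 4. The re-induction, maintenance, end-of-treatment and follow-up cells are blank, and the EDC timepoint is given as baseline alone.

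**The concern.** The protocol tells participants to avoid conception for months after the last dose, yet its one explicit rule for reporting a pregnancy stops at 30 days. The open-ended clause in 7.4.2 might fill the gap, but it does not define exposure and does not mention partners. A site reading 7.4 literally could close its pregnancy reporting at day 30. A site relying on 7.4.2 could continue. Both would be following the protocol.

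At stake is the capture of exposed pregnancies and their outcomes. A healthy or uneventful pregnancy never triggers the late-SAE rule, and no section requires the outcome of a reported pregnancy to be followed. No pregnancy test is listed after the last dose, so later conceptions would come to light only if someone asks or the participant volunteers it.

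The Table 7 conflict is a second, smaller matter. The calendar and EDC schedule are what sites commonly work from, and here the cells say less than the footnote and the text.

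**Working it through.** The protocol gives no figure for this gap, so the check is calendar arithmetic. One month is taken as 365.25/12 = 30.44 days.

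**Inputs**
- Explicit reporting window: 30 days after the last dose of treatment (7.4).
- Contraception: 6 months after ipilimumab; 5 months (women) or 7 months (men) after nivolumab (3.1.11).
- Schedule (5 and 5.1): four ipilimumab doses every 3 weeks. Responders then have up to 8 maintenance doses every 12 weeks. Non-responders have four combination doses every 3 weeks, then up to 7 maintenance doses every 12 weeks.

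**Post-treatment days outside the window, ipilimumab last**
- 6 × 30.44 = 183 days.
- 183 − 30 = 153 days outside; 153/183 = 84%.

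**The same days as a share of first dose to end of contraception**
- Last dose for a completing responder: week 12 + 7 × 12 = week 96, day 672.
- Last dose for a completing re-induced patient: week 24 + 6 × 12 = week 96, also day 672.
- Completer: 153/(672 + 183) = 153/855 = 18%.
- Stopping after four ipilimumab doses (last dose week 9, day 63): 153/(63 + 183) = 153/246 = 62%.

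**When the nivolumab periods matter**
- The last planned nivolumab dose is at week 12 + 9 = week 21, day 147. Seven months later is day 147 + 213 = 360, about week 51. A completer is still on treatment then (to week 96), so the nivolumab period lies wholly inside the reporting window.
- If therapy ends with re-induction, the 7-month period for men applies: (213 − 30)/213 = 183/213 = 86% of post-treatment days fall outside, or 183/360 = 51% counted from first dose.
- For women whose two drugs end on the same day, the 6-month ipilimumab period is the longer one and the 84% figure applies. The 5-month period governs only if ipilimumab stopped more than about a month (183 − 152 = 31 days) before the last nivolumab dose, as section 6.7 could allow. It would give (152 − 30)/152 = 122/152 = 80%.

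**Table 7 against its footnote, at maximum dosing**

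| | Day 1 visits | Marked in B-HCG row | Unmarked | Required by footnote e and 10.2 |
|---|---|---|---|---|
| Responder | 4 + 8 = 12 | 4 | 8 | 12 |
| Re-induced | 4 + 4 + 7 = 15 | 4 | 11 | 15 |

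**The case against.** **Section 7.4.2 has no time limit, so nothing is lost after day 30.** This stands in part. A reader might infer from 7.4 that pregnancies are reportable only to 30 days. The documents do not support so flat a reading, because 7.4.2 is open-ended and 7.4 extends SAE reporting to other individuals exposed to study drug. But 7.4.2 does not say whether conception after the last dose is exposure, and it is silent on partners. The result is an inconsistency rather than a proven absence of reporting.

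**Birth defects are SAEs and late related SAEs are reportable.** True, but that rule needs an SAE and a suspected causal link. It does not reach an uncomplicated pregnancy. Section 7.4.4 also makes the late rule less clear, since its own suspected-causality sentence refers to SAEs within 30 days of the last dose.

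**Testing is already required.** This stands. A reader looking at the blank cells might infer that re-induction and maintenance carry no pregnancy testing, and that a participant could be dosed for two years untested. Footnote e belongs to Table 7 and, with section 10.2, requires a test on day 1 of each cycle; both phases are organised in cycles. What remains is a conflict between cells and footnote. Some nearby rows (concurrent medications, adverse event evaluation) look damaged in the text extraction, so the blanks should be confirmed in the source table. The physical examination row does keep its re-induction and maintenance marks and an every-visit EDC entry.

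**The scale is small.** This also stands: 13 patients are planned and pregnancies should be few.

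**Conclusion.** The inconsistency is real and worth correcting as a safety-reporting matter. Sections 7.4, 7.4.2 and 3.1.11 do not define one window, and a participant or partner pregnancy conceived in months 2 to 6 after ipilimumab is not clearly captured. About 84% of post-treatment contraception days lie outside the explicit window when ipilimumab is the last drug.

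A reader might go further and infer that most of a stated fetal-risk period is unmonitored. The documents do not support that. They state contraception periods, not a fetal-risk period. Counted from first dose, the share outside the window is about 18% for a completer and becomes a majority only for those who stop early. Nor do the 5- and 7-month periods enlarge the gap for everyone: responders receive no nivolumab, and a re-induced completer's nivolumab period ends while still on treatment.

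The figures assume planned dosing without delays and months of 30.44 days. They also assume that the 6-month ipilimumab period applies to the participant; the sentence for men in 3.1.11 is addressed to men receiving nivolumab, so its application to men given ipilimumab alone is itself unclear. The protocol gives no expected number of pregnancies; that they would be rare is an assumption. The primary response endpoint and its test are not affected.

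**What to change.** 1. Reconcile the pregnancy reporting window in 7.4 with the contraception periods in 3.1.11. Make 7.4.2 refer to the same window, state whether conception after the last dose counts as exposure, name both participants and partners, and require the pregnancy outcome to be reported.
2. Capture this at contacts that already exist: the 3-monthly follow-up visits for patients in remission, and the relapse and survival contacts in 10.3 for patients who progress or start other therapy, who would otherwise be missed.
3. Reconcile the B-HCG cells and EDC timepoint in Table 7 with footnote e and section 10.2.

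The cost is wording in two subsections, a pregnancy question at existing contacts, and corrected calendar cells. Testing on day 1 of each cycle is already required, so item 3 need add no procedure if the cells are brought into line with the text. The downside is a longer reporting duty for rare events, with some added effort to obtain outcomes for partner pregnancies. No analysis or sample-size figure changes.

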# 7.4.1 SAE Definition for Reporting to BMS

An SAE is any adverse event, without regard to causality, that is life-threatening (i.e., causes an immediate risk of death) or that results in any of the following outcomes: death; in-patient hospitalization or prolongation of existing hospitalization; persistent or significant disability or incapacity (i.e. substantial disruption of the ability to conduct normal life functions); or a

\* For participants enrolled and actively participating in the study *or* for AEs occurring within 30 days of the last intervention, the AE should be reported within 1 business day of learning of the event.

congenital anomaly or birth defect. Any other medical event that, in the medical judgment of the Principal Investigator, may jeopardize the subject or may require medical or surgical intervention to prevent one of the outcomes listed above is also considered an SAE. A planned medical or surgical procedure is not, in itself, an SAE.

# 7.4.2 Exposure During Pregnancy, Exposure During Lactation, Occupational Exposure

Even though there may not be an associated SAE, occupational exposure to ipilimumab +/-nivolumab or exposure during pregnancy or lactation is reportable to BMS.

# 7.4.3 Exclusions from SAE Reporting Requirements

Specifically excluded from the reporting requirements for SAEs under this provision is any SAE identified in the Protocol as anticipated to occur in the Study population at some frequency independent of drug exposure, unless the Principal Investigator assesses such an event as related to study medication. Also, specifically excluded from the reporting requirements is any SAE judged by the Overall Investigator to represent progression of the malignancy under study, unless it results in death within the SAE Reporting Period.

# 7.4.4 SAE Reporting Period

The SAEs that are subject to this reporting provision are those that occur from after the first dose of study medication(s) through 30 calendar days after the last administration of the study medication(s). In addition, if a Sponsor-Investigator becomes aware of an SAE occurring within 30 days of last dose of study medication the Sponsor-Investigator should report that SAE to BMS if the Sponsor-Investigator suspects a causal relationship between the study drug and the SAE. In addition, if the investigator determines that an SAE is associated with study procedures, the investigator must record this causal relationship in the source documents.

# 7.5 Reporting to the Food and Drug Administration (FDA)

The Sponsor-Investigator will be responsible for all communications with the FDA. The Sponsor-Investigator will report to the FDA, regardless of the site of occurrence, any serious adverse event that meets the FDA's criteria for expedited reporting following the reporting requirements and timelines set by the FDA.

# 7.6 Reporting to Hospital Risk Management

Participating investigators will report to their local Risk Management office any participant safety reports, sentinel events or unanticipated problems that require reporting per institutional policy.

# 7.7 Routine Adverse Event Reporting

All Adverse Events **must** be reported in routine study data submissions to the PI on the toxicity case report forms. **AEs reported through expedited processes (e.g., reported to the IRB,** 

FDA, etc.) must also be reported in routine study data submissions.

## 8. PHARMACEUTICAL INFORMATION

A list of the adverse events and potential risks associated with the investigational or other agents administered in this study can be found in Section 7.1.

# 8.1 Ipilimumab

# 8.1.1 Description

Ipilimumab is a fully human monoclonal immunoglobulin that binds to CTLA-4 and inhibits its interaction with ligands on antigen presenting cells. Ipilimumab has a terminal half-life of approximately 15.4 days. A population PK analysis of ipilimumab (n=785) demonstrated that the PK of ipilimumab is linear and exposures are dose proportional across the tested dose range of 0.3 to 10 mg/kg.

#### 8.1.2 Form

Injection: 50 mg/10 mL (5 mg/mL) as a clear to slightly opalescent, colorless to pale-yellow solution in a single-use vial.

# 8.1.3 Storage and Stability

Ipilimumab should be stored under refrigeration at 2°C to 8°C (36°F to 46°F). Protect from light by storing in the original carton until time of use. Do not freeze or shake.

## 8.1.4 Compatibility

When both ipilimumab and nivolumab are to be administered on the same day, separate infusion bags and filters must be used for each infusion. Nivolumab is to be administered first. The nivolumab infusion must be promptly followed by a saline flush to clear the line of nivolumab before starting the ipilimumab infusion. The second infusion will always be ipilimumab and will start no sooner than 30 minutes after completion of the nivolumab infusion.

# 8.1.5 Handling

Qualified personnel, familiar with procedures that minimize undue exposure to themselves and the environment, should undertake the preparation, handling, and safe disposal of the chemotherapeutic agent in a self-contained and protective environment.

The product storage manager should ensure that the study drug is stored in accordance with the environmental conditions (temperature, light, and humidity) as determined by the sponsor. If concerns regarding the quality or appearance of the study drug arise, do not dispense the study drug and contact the sponsor immediately.

Investigational product documentation must be maintained that includes all processes required to ensure drug is accurately administered. This includes documentation of drug storage, administration and, as applicable, storage temperatures, reconstitution, and use of required processes (eg, required diluents, administration sets).

Please refer to the current IB/pharmacy reference sheets for storage, handling and preparation instructions.

# 8.1.6 Availability

Ipilimumab will be provided by BMS from investigational supply.

# 8.1.7 Preparation

Please refer to the current IB/pharmacy reference sheets for preparation instructions. Study product should be prepared and dispensed by an appropriately qualified and experienced member of the study staff (eg, physician, nurse, physician's assistant, practitioner, pharmacist, or medical assistant) as allowed by local, state, and institutional guidance. Only qualified personnel who are familiar with procedures that minimize undue exposure to them and to the environment should undertake the preparation, handling, and safe disposal of biologic agents.

Dosing of ipilimumab will be based on the patient's weight in kilograms (kgs). All patients should be weighed within 3 days prior to dosing for every cycle to ensure they did not experience either a weight loss or gain >10% from the weight used for the last dose calculation. If the patient experienced either a weight loss or gain >10% compared to the weight used for the last dose calculation, the amount of study drug must be recalculated.

Vials are for single use only. Any unused portion of the solution must be discarded in a biohazard waste disposal container with final disposal according to accepted local and national standards of incineration.

